### **Randomization (Week 0)**

At baseline (Visit 3, Week 0), eligibility of the subjects (Sections [5.1](#) to [5.3](#)) to participate in the trial must be confirmed. Eligible subjects will be randomized 1:1:1:1:1 to 1 of 5 treatment groups: LEO 138559 (4 different dose regimens) or placebo. Randomization will be based on a permuted block design, stratified by baseline disease severity (baseline vIGA-AD score), region (Japan, Other countries), prior use of biologics or systemic JAK inhibitors for AD (Yes/No), and baseline biopsy status (willingness to provide biopsies: Yes/No). IRT will be used to control randomization and stratification factors.

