## 6.3 Treatment assignment and blinding

### 6.3.1 Treatment assignment

Subjects who meet all the eligibility criteria (Sections 5.1 to 5.3) will be randomized at baseline (Day 1) to receive treatment according to 1 of the treatment regimens outlined in Section 6.2.

Treatment assignment will be pre-planned according to a computer-generated randomization schedule in a 1:1:1:1:1 ratio (4 LEO 138559 dose regimens and 1 placebo regimen), based on a permuted block design and stratified by baseline disease severity (baseline vIGA-AD score), region (Japan, Other countries), prior use of biologics or systemic JAK inhibitors for AD (Yes/No), and baseline biopsy status (willingness to provide biopsies: Yes/No).

IRT will be used to control randomization and stratification factors, along with IMP supply chain, and expiry tracking.

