## 9 Scientific rationale for trial design and appropriateness of assessments

### 9.1 Scientific rationale for trial design

This is a randomized, double-blind, placebo-controlled, multi-site, parallel-group, dose-finding trial, which will be conducted in accordance with the protocol, ICH GCP, and applicable regulatory requirements.

The trial will be conducted at multiple trial sites located in Europe, North America, and Japan.

Patients with AD represent a heterogeneous patient population with disease severity ranging from mild to severe. To mitigate any potential difference in trial outcome based on baseline characteristics, eligibility criteria for inclusion have been carefully selected and trial subjects will be randomized according to a stratified, permuted block design. The randomization will minimize selection bias and ensure that the effect of treatment is not confounded by baseline factors. The stratified permuted block design and the inclusion of prognostic baseline factors in the analysis will improve the precision of the estimated treatment effect.

The most important inclusion criteria for entry into the trial is a diagnosis of AD (as defined at screening by the Hanifin and Rajka 1980 criteria (62)) and history of AD for at least 1 year, to ensure correct diagnosis and rule out differential diagnoses.

Patients with moderate-to-severe AD with inadequate response to treatment with TCS ( $\pm$ TCI as appropriate), or for whom these topical AD treatments are medically inadvisable, are the target population for treatment with LEO 138559. Only adults (aged 18–75 years) are included. In order to evaluate any efficacy of LEO 138559, subjects in the trial cannot be on concomitant medication for AD or have diseases that may influence the evaluation of AD signs and symptoms.

LEO Pharma plans to evaluate LEO 138559 administered SC in 4 different dose regimens.

The following LEO 138559 dose regimens will be included:

- Dose regimen 1: LEO 138559 [REDACTED] mg SC Weeks 0, 1, 2, 3 and then [REDACTED] mg SC Q2W from Week 4.
- Dose regimen 2: LEO 138559 [REDACTED] mg SC Weeks 0, 1, 2 and then [REDACTED] mg SC Q2W from Week 4.
- Dose regimen 3: LEO 138559 [REDACTED] mg SC Weeks 0 and 2 and then [REDACTED] mg SC Q2W from Week 4.
- Dose regimen 4: LEO 138559 [REDACTED] mg SC Weeks 0 and 2 and then [REDACTED] mg SC Q2W from Week 4.

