### **11.3.4 Demographics and other baseline characteristics**

Descriptive statistics of demographics and other baseline characteristics will be presented for all randomized subjects and by treatment group. Presentations of age, sex, ethnicity, race, and baseline EASI score by treatment group will also be given by baseline disease severity (baseline vIGA-AD score), region (Japan, Other countries), prior use of biologics or systemic JAK inhibitors for AD (Yes/No), and baseline biopsy status (willingness to provide biopsies: Yes/No).

Other baseline characteristics include height, weight, body mass index, duration of AD, concurrent diagnoses (from medical history and indications for concomitant medication), concomitant medication, and previous AD treatments.

THIS DOCUMENT CONTAINS CONFIDENTIAL INFORMATION AND MUST NOT BE COPIED OR MADE AVAILABLE TO ANY THIRD PARTY WITHOUT THE PRIOR WRITTEN CONSENT OF THE LEO PHARMA GROUP

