### 11.3.8 Primary estimand analysis

#### 11.3.8.1 Analysis of primary estimand for continuous endpoints

##### Primary analysis

Data collected after permanent discontinuation of IMP or after initiation of rescue treatment will be excluded from the analysis and “treated as missing”. Missing data and data “treated as missing” will be split into two groups:

1. Data “treated as missing” due to permanent discontinuation of IMP due to lack of efficacy, an AE related to worsening of AD, or rescue treatment.
2. Missing data or data “treated as missing” for other reasons than permanent discontinuation of IMP due to lack of efficacy, an AE related to worsening of AD, or rescue treatment.

The first group will have their missing values imputed using last observation carried forward. This reflects an assumption that subjects that need rescue treatment or permanently discontinue IMP due to lack of efficacy or an AE related to worsening of AD must be expected not to improve going forward even if they had continued IMP.

The second group will be imputed using MI (100 iterations) under a MAR assumption within each treatment group. All subject-level data observed prior to the occurrence of an intercurrent event will be used to inform the imputation models. Further details regarding the specification of the imputation models, including choice of seed, will be specified in the SAP.

The imputed datasets will be combined to create 100 complete datasets. For each of the 100 complete datasets, the response will be analyzed using an ANCOVA model adjusted for treatment, baseline disease severity (baseline vIGA-AD score), region (Japan, Other

THIS DOCUMENT CONTAINS CONFIDENTIAL INFORMATION AND MUST NOT BE COPIED OR MADE AVAILABLE TO ANY THIRD PARTY WITHOUT THE PRIOR WRITTEN CONSENT OF THE LEO PHARMA GROUP

countries), and prior use of biologics or systemic JAK inhibitors for AD (Yes/No). The model will also be adjusted for the baseline value of the dependent variable.

The pooled estimate of the difference in the LSmean change from baseline, along with the associated 95% CIs and nominal p-values will be presented. Inference will be based on applying Rubin's rules to the estimates and standard errors from the ANCOVA analysis of the imputed datasets.

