#### **11.3.8.2 Analysis of primary estimand for binary endpoints**

Subjects receiving rescue treatment or who have permanently discontinued IMP due to lack of efficacy, or the occurrence of an AE related to worsening of AD, prior to the endpoint of interest, are defined as non-responders, reflecting an assumption that the occurrence of such intercurrent events indicates a failure of the randomized treatment.

Data observed after the permanent discontinuation of IMP for reasons besides lack of efficacy or the occurrence of an AE related to worsening of AD will be excluded from the analysis and treated as missing. Missing data and data treated as missing will be imputed using MI (100 iterations) under a MAR assumption within each treatment group. All subject-level data observed prior to the occurrence of an intercurrent event will be used to inform the imputation

THIS DOCUMENT CONTAINS CONFIDENTIAL INFORMATION AND MUST NOT BE COPIED OR MADE AVAILABLE TO ANY THIRD PARTY WITHOUT THE PRIOR WRITTEN CONSENT OF THE LEO PHARMA GROUP

models. Further details regarding the specification of the imputation models will be specified in the SAP.

The 100 complete datasets will be analyzed based on a logistic regression model, including treatment, baseline disease severity (vIGA-AD score at baseline), region (Japan, Other countries), prior use of biologics or systemic JAK inhibitors for AD (Yes/No) and the baseline value of the endpoint as a covariate. The logistic regression model will be used to estimate the risk, risk difference, and associated 95% CI based on the standardized estimator presented in Bartlett (80). For the analysis of the vIGA-AD responder endpoints, baseline disease severity will not be included as a covariate in the logistic regression model.

The pooled estimate of the risk difference, along with the associated 95% CIs and nominal p-values will be presented. Inference will be based on applying Rubin's rules to the estimates obtained from the analysis of the imputed data sets using the standardized estimator.

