### 11.3.9 Supplementary estimand analysis

#### 11.3.9.1 Analysis of hypothetical supplementary estimand for continuous endpoints

##### Primary analysis

Data collected after permanent discontinuation of IMP or after initiation of rescue treatment will be excluded from the analysis and “treated as missing”. Missing data and data “treated as missing” will be split into two groups:

1. Data “treated as missing” due to discontinuation due to lack of efficacy, an AE related to worsening of AD, or rescue treatment.
2. Missing data or data “treated as missing” for other reasons than discontinuation due to lack of efficacy, an AE related to worsening of AD, or rescue treatment.

The first group will have their missing values imputed using an ANCOVA model adjusting for treatment, region, and time as a continuous covariate. Noise will be added to the predicted values from the imputation model. The imputation will be repeated 100 times. Further details regarding the imputation model, including choice of seed, will be specified in the SAP.

The second group will be imputed using MI (100 iterations) under a MAR assumption within each treatment group. All subject-level data observed prior to the occurrence of an intercurrent event will be used to inform the imputation models. Further details regarding the specification of the imputation models will be specified in the SAP.

THIS DOCUMENT CONTAINS CONFIDENTIAL INFORMATION AND MUST NOT BE COPIED OR MADE AVAILABLE TO ANY THIRD PARTY WITHOUT THE PRIOR WRITTEN CONSENT OF THE LEO PHARMA GROUP

The imputed datasets will be combined to create 100 complete datasets. For each of the 100 complete datasets, the response will be analyzed using an ANCOVA model adjusted for treatment, baseline disease severity (baseline vIGA-AD score), region (Japan, Other countries), and prior use of biologics or systemic JAK inhibitors for AD (Yes/No). The model will also be adjusted for the baseline value of the dependent variable.

The pooled estimate of the difference in the LSmean change from baseline, along with the associated 95% CIs and nominal p-values will be presented. Inference will be based on applying Rubin's rules to the estimates and standard errors from the ANCOVA analysis of the imputed datasets.

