### **11.3.9.2 Analysis of second supplementary estimand for continuous endpoints**

#### **Primary analysis**

All observed data will be included in the analysis, including data observed after the occurrence of intercurrent events.

Missing data will be imputed using MI (100 iterations) under a MAR assumption within each treatment group. All observed data will be used to inform the imputation model. Further details regarding the specification of the imputation models will be detailed in the SAP.

For each of the 100 complete datasets, the response will be analyzed using an ANCOVA model adjusted for treatment, baseline disease severity (baseline vIGA-AD score), region (Japan, Other countries), and prior use of biologics or systemic JAK inhibitors for AD (Yes/No). The model will also be adjusted for the baseline value of the dependent variable.

The pooled estimate of the difference in the LSmean change from baseline, along with the associated 95% CIs and nominal p-values will be presented. Inference will be based on applying Rubin's rules to the estimates and standard errors from the ANCOVA analysis of the imputed datasets.

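### The ANCOVA models leave out baseline biopsy status, one of the four randomization strata, without a stated reason; adding it before unblinding is a low-cost refinement with a small and uncertain gain

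*Combined protocol and SAP*

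**What the plan says.** Section 6.3.1 describes permuted blocks stratified by baseline vIGA-AD, region, "prior use of biologics or systemic JAK inhibitors for AD (Yes/No), and baseline biopsy status (willingness to provide biopsies: Yes/No". Section 4.1 (Randomization) gives the same four factors and says that the IRT controls them. Section 11.3.4 presents selected baseline characteristics by all four, again ending with "and baseline biopsy status (willingness to provide biopsies: Yes/No".

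The efficacy models use three of the four:

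- 11.3.8.1, primary continuous analysis: "the response will be analyzed using an ANCOVA model adjusted for treatment, baseline disease severity (baseline vIGA-AD score), region (Japan, Other", then prior therapy and the baseline value of the endpoint.
- 11.3.9.1, hypothetical supplementary analysis: "For each of the 100 complete datasets, the response will be analyzed using an ANCOVA model adjusted for treatment, baseline disease severity", with the same remaining terms.
- 11.3.9.2, second supplementary analysis: "adjusted for treatment, baseline disease severity (baseline vIGA-AD score), region (Japan, Other countries), and prior use of biologics or systemic JAK inhibitors", plus the baseline value.
- 11.3.8.2 and 11.3.9.3, logistic models: the same three factors (for example "logistic regression model, including treatment, baseline disease severity (vIGA-AD score at baseline), region (Japan, Other") plus the baseline value, with severity dropped for vIGA-AD responders.
- 11.3.8.3 and 11.3.9.4, Gray's test and the log-rank test: stratified by the same three.

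The nearest thing to a covariate rationale is in Section 9.1: "The stratified permuted block design and the inclusion of prognostic baseline factors in the analysis will improve the precision of the estimated treatment effect". It does not say which of the stratification factors are regarded as prognostic. Section 8.6 says that biopsies are taken at selected sites, with consent, up to a global cap of 75 subjects.

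**The concern.** Stratified randomization balances biopsy status across arms, so the true sampling variance of a treatment difference excludes most of the variation due to that factor. An analysis without the factor leaves that variation in the residual. If biopsy status predicts EASI change, the reported standard error is therefore larger than the true one, and some of the precision gained by stratifying is lost. Willingness to be biopsied arises at selected sites and among volunteers, so it could partly mark site or patient type. That is a plausible route to prognostic value, but not a documented one.

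What is at stake is a little precision, chiefly for regimen 4 versus placebo (67.4% stated power) and regimen 1 versus 2 (49.7%). Regimens 1 to 3 versus placebo have stated power of 97.2% or more, so there is little to gain there.

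**Working it through.** **Inputs from the plan.** 250 subjects, 50 per arm; two-sided 5% level; Panel 14 Week 16 means of -20.7, -15.3, -13.8 and -10.0 for regimens 1 to 4 and -3.5 for placebo; variance 111.0 (SD 10.54); event or withdrawal rates of 20, 20, 30, 40 and 40%; Panel 15 nominal power.

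**Assumptions.** The partial R² of biopsy status is not given; 1% and 5% are used. The share of biopsy-Yes subjects is taken as 75/250 = 30%, from the cap.

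**Reproducing Panel 15.** Use power = Φ(|difference|/SE - 1.960), with each arm reduced to 50 × (1 - event rate). For regimen 4 versus placebo, SE = 10.54 × √(1/30 + 1/30) = 2.72, and 6.5/2.72 = 2.39, giving 66.6% against 67.4% stated. Regimens 1, 2 and 3 versus placebo give 100%, 99.6% and 97.6% against about 100%, 99.1% and 97.2%. Regimen 1 versus 2 comes out at 63% against 49.7%, so this shortcut does not reproduce it. A complete-case simulation on the bounded percent-change scale gave 51.2% (assumed baseline EASI mean 32, SD 13, slope -0.3). An attempt at the described within-arm imputation gave only about 48 to 58% for regimen 4, because the resampled baselines and the baseline coefficient are not published. The steps below therefore scale the stated power and do not replace it.

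**Cost in degrees of freedom.** The ANCOVA has 1 intercept + 4 treatment + 1 severity + 1 region + 1 prior therapy + 1 baseline = 9 parameters, so 250 - 9 = 241 residual df. With biopsy status there are 240.

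**Effect on power, complete data.** The noncentrality behind the stated power is 1.960 + z(0.674) = 2.411 for regimen 4 versus placebo, and 1.960 + z(0.497) = 1.952 for regimen 1 versus 2. The SE ratio is √[(1 - R²) × 241/240], and new power = Φ(noncentrality/SE ratio - 1.960).

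| Partial R² | SE ratio | Regimen 4 vs placebo | Regimen 1 vs 2 |
|---|---|---|---|
| 0 | 1.002 | 67.2% | not computed |
| 1% | 0.997 | 67.7% | 49.9% |
| 5% | 0.977 | 69.4% | 51.6% |

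Break-even is where (1 - R²) × 241/240 = 1, that is R² = 1/241 ≈ 0.4%.

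**What these R² values mean.** The Yes-No difference in residual SDs is √[R²/(1 - R²)/(0.30 × 0.70)] = 0.22 at 1% and 0.50 at 5%. The lower value is the more plausible.

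**With multiple imputation.** A simulation on the change scale (Panel 14 means, plan variances and event rates, within-arm imputation, biopsy status in the ANCOVA only) gave SE ratios of 0.998 and 0.991 for regimen 4 versus placebo. That corresponds to about 67.5% and 68.2%. The conversion is approximate: the simulated tests had a size of about 2.4%, and the primary endpoint is percent change.

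**Simulation margin of Panel 15.** 1.96 × √(0.674 × 0.326/1000) = 2.9 points. The largest gain shown is 69.4 - 67.4 = 2.0 points.

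**Bias and type I error.** Stratified blocks were simulated with complete data and an assumed residual SD of 37 percentage points. With the factor omitted, type I error was 4.9, 4.6, 4.7 and 4.4% for biopsy effects of 0, 5, 10 and 20 points. With it included, it was 5.0, 4.7, 4.9 and 4.9%. At 20 points (partial R² = 400 × 0.21/(400 × 0.21 + 37²) = 5.8%), the mean model SE without the factor was 7.64 against an empirical 7.45. With the factor it was 7.41 against 7.42. At a true difference of 18 points, power was 65.7% without and 67.7% with.

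**Imputation models.** In the simulations, adding biopsy status to the within-arm imputation as well gave about 65.2 to 67.7% at R² = 1% and 66.1 to 68.5% at 5%, depending on the model. The largest model had 12 parameters for about 50 × 0.6 = 30 observed Week 16 values per arm.

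**Time-to-event strata.** Three two-level factors make 8 strata, or 100/8 = 12.5 subjects on average in a two-arm comparison. Four make 16 strata, or about 6.

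**The case against.** The strongest reply is that the choice may be deliberate. Section 9.1 speaks of prognostic factors, not of every stratification factor. The three that are used are plausible prognostic factors and appear consistently across the models. Biopsy status records willingness to join an exploratory component, so stratifying on it may serve only to balance that subset over five arms. Nothing in the documents shows that it predicts EASI change, and listing it in the baseline tables does not commit the sponsor to adjusting for it. This stands as a possible rationale, but the protocol does not state it. Imputation details are deferred to the SAP, whereas the analysis covariates are set in Section 11. A reason given in a separate SAP would answer the question.

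A reader might also infer that adding the factor is a free gain. It is not: below a partial R² of about 0.4% it loses a fraction of a point, and the documents do not show which side of that line the factor falls on. Nor does the case for the ANCOVA carry over to every model. The imputation step can lose about 2 points, the stratified tests would have sparse strata, and no gain has been computed for the logistic models.

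**Conclusion.** The point holds as a minor refinement. One of four randomization strata is missing from the three ANCOVA models and no reason is given. A reader might infer that the primary comparison is biased or its error rate inflated. The documents do not support that: the factor is balanced by design, and omitting it can only make the tests slightly conservative. For regimen 4 versus placebo, adding it changes power by about -0.2 to +2.0 points for partial R² from 0 to 5% with complete data, and by less under multiple imputation. These figures rest on an assumed R², and the implied Yes-No differences also on the assumed 30% share. All the changes lie inside Panel 15's own margin. The case for the change is that the analysis then follows the randomization at almost no cost, not that a material gain in power is expected.

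**What to change.** Before unblinding, add baseline biopsy status (Yes/No, as randomized in the IRT) as a main effect to the ANCOVA models in 11.3.8.1, 11.3.9.1 and 11.3.9.2. Describe and justify the change in an amendment, the SAP and/or the CTR, as Section 11.3.1 requires.

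Do not extend it to the per-arm imputation models or to the stratified Gray and log-rank tests. The logistic models can stay as they are, since no gain has been shown for them.

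The cost is one residual degree of freedom and a short documented change. No new data are needed.

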### **Sensitivity analysis**

A sensitivity analysis will be performed for the change and percent change in EASI score from baseline to Week 16 endpoints.

A tipping point analysis will be performed based on implementing a delta-adjusted MI approach. The delta-adjusted imputation approach allows for missing data to be imputed under a MNAR assumption. Heuristically, the imputation strategy, adjusts/shifts the parameters of the MAR distribution based on the value of a numeric offset term, denoted by delta. The tipping point analysis will adjust the values of the parameters in the MAR distribution representing the mean change in EASI score from baseline to Week 16. The analysis will assess how robust the results of the main analysis are to varying departures from the MAR assumption within each treatment group. The range of the shift parameter for the treatment arms will be specified in the SAP along with the seed, the MAR imputation strategy, and the number of imputations.

### *Supplementary analysis*

For the continuous endpoints related to the EASI score, the primary analysis will be repeated for all protocol-defined visit weeks.

#### **11.3.8.2 Analysis of primary estimand for binary endpoints**

Subjects receiving rescue treatment or who have permanently discontinued IMP due to lack of efficacy, or the occurrence of an AE related to worsening of AD, prior to the endpoint of interest, are defined as non-responders, reflecting an assumption that the occurrence of such intercurrent events indicates a failure of the randomized treatment.

Data observed after the permanent discontinuation of IMP for reasons besides lack of efficacy or the occurrence of an AE related to worsening of AD will be excluded from the analysis and treated as missing. Missing data and data treated as missing will be imputed using MI (100 iterations) under a MAR assumption within each treatment group. All subject-level data observed prior to the occurrence of an intercurrent event will be used to inform the imputation

THIS DOCUMENT CONTAINS CONFIDENTIAL INFORMATION AND MUST NOT BE COPIED OR MADE AVAILABLE TO ANY THIRD PARTY WITHOUT THE PRIOR WRITTEN CONSENT OF THE LEO PHARMA GROUP

models. Further details regarding the specification of the imputation models will be specified in the SAP.

The 100 complete datasets will be analyzed based on a logistic regression model, including treatment, baseline disease severity (vIGA-AD score at baseline), region (Japan, Other countries), prior use of biologics or systemic JAK inhibitors for AD (Yes/No) and the baseline value of the endpoint as a covariate. The logistic regression model will be used to estimate the risk, risk difference, and associated 95% CI based on the standardized estimator presented in Bartlett (80). For the analysis of the vIGA-AD responder endpoints, baseline disease severity will not be included as a covariate in the logistic regression model.

The pooled estimate of the risk difference, along with the associated 95% CIs and nominal p-values will be presented. Inference will be based on applying Rubin's rules to the estimates obtained from the analysis of the imputed data sets using the standardized estimator.

